- Measure compliance with the implementation of a computerized lung protective ventilation protocol at 11 Intermountain Healthcare hospitals

Specific Aim #1: Determine if the implementation of lung protective ventilation with a 6 ml/kg PBW tidal volume ventilation protocol on initiation of mechanical ventilation improves ventilator free days (VFDs) to day 28 (primary outcome), mortality, and secondary outcomes in **patients with acute respiratory failure requiring mechanical ventilation**.

- Process for Aim #1: Standardized management of mechanical ventilation and outcomes will be measured through electronic medical record data. A detailed plan on these metrics has been included (see research strategy for specific aims).
- **Hypothesis 1:** Deployment of the ventilation protocol will result in improvements in the number of VFDs to day 28, mortality, hospital discharge disposition, healthcare utilization and costs of care in patients with acute respiratory failure requiring mechanical ventilation.

Specific Aim #2: Determine if the implementation of lung protective ventilation with a 6 ml/kg PBW tidal volume ventilation protocol on initiation of mechanical ventilation improves VFDs to day 28, mortality, and secondary outcomes in **patients with ARDS requiring mechanical ventilation**.

- Process for Aim #2: Standardized management of mechanical ventilation for patients with ARDS and outcomes will be measured through electronic medical record data. A detailed plan on these metrics has been included (see research strategy for specific aims).
- Hypothesis 2: Deployment of the ventilation protocol in patients with ARDS will result in improvements in the number of VFDs to day 28, mortality, hospital discharge disposition, healthcare utilization and costs of care.

Specific Aim #3: Characterize protocol implementation of the high positive end expiratory pressure protocol (PEEP) and outcomes for mechanically ventilated patients with moderate or severe hypoxemia and ARDS.

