- Process for Aim #3: Patients with ARDS will be analyzed based on hypoxemia conditions (as defined by their PaO₂ to FiO₂ ratio) using 3 classifications: mild (201-300), moderate (101-200), and severe (≤100). This subgroup analysis will evaluate protocol implementation of the high versus low positive end expiratory pressure (PEEP) protocol and assess relationship with patient outcomes. Data from Intermountain ICUs in 2014 have shown that approximately 500 patients meet the criteria for "severe" hypoxemia. Patients with moderate and severe hypoxemia will be identified to determine the frequency of high PEEP protocol usage (which is the recommendation in the protocol). Implementation of the high PEEP protocol will be based upon clinician discretion. We will assess outcomes in the 4 hypoxemia sub-groups noted above using a stratified Kaplan–Meier curve to determine differences in mortality using log rank statistics.
- Hypothesis 3: A high PEEP strategy in patients with moderate to severe hypoxemia and ARDS will improve outcomes.

Specific Aim #4: Measure compliance of the computerized lung protective ventilation protocol after implementation across Intermountain Healthcare's 11

hospitals that manage mechanically ventilated patients with acute respiratory failure.

- Process for Aim #4: Tool utilization and compliance will test the ability
 of a healthcare system to introduce this proven lung protective
 ventilation protocol in a new electronic medical record in a controlled
 clinical environment. To ensure that this is successful, [name] will
 identify local champions to train and educate the healthcare providers.
- Hypothesis 4: Healthcare providers will utilize the computerized ventilation protocol and will comply with protocol instructions.

Study Design:

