Efficacy of a high PEEP strategy for patients requires identifying patients with moderate or severe ARDS, determining protocol compliance, and measuring outcomes. Determination of ARDS using the Berlin Definition²³ requires acute respiratory failure not fully explained by cardiac failure or fluid overload within one week of a known clinical insult, bilateral opacities on chest radiology imaging not fully explained by effusions, lobar/lung collapse, or nodules, and $PaO_2/FIO_2 \le 300$ mm Hg with PEEP or CPAP ≥ 5 cm H₂O. Applying these criteria to identify ARDS in a large pragmatic study with a target enrollment of approximately 3,500 patients is a significant challenge. We will focus on defining ARDS among those patients with mild, moderate, or severe hypoxemia as defined by a PaO_2 to FIO_2 ratio ≤ 300 and evaluate chest radiographs for bilateral infiltrates in that group. Then we will evaluate implementation of the high PEEP strategy and outcomes in the group of patients with ARDS who have a PaO_2 to FIO_2 ratio ≤ 200 . Even though a high PEEP strategy is recommended for moderate to severe ARDS as

defined by a PaO₂/FIO₂ ≤ 200, this is not strictly applied clinically based on our review of ARDS Network study data (**Figure 2**). Implementation of the high PEEP protocol for moderate to severe ARDS is left up to the clinician in the computerized mechanical ventilation protocol. By performing a sub-group analysis we will characterize the utilization of a high PEEP strategy in patients with moderate or severe ARDS at Intermountain Healthcare hospitals. Lastly, the benefit of segmenting the data into categories "mild", "moderate", and "severe" hypoxemia, is that it will allow our team to use a stratified Kaplan–Meier curve to assess differences in mortality using log rank statistics. This will directly show the relationship between hypoxemia, treatment and mortality. New findings from Specific Aim #3 may drastically influence the standard of care within Intermountain Healthcare and internationally.

Research Strategy for Specific Aim 4

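### Aim 3 plans a log-rank over 4 hypoxaemia sub-groups where three are defined, and does not say which groups are compared, so it specifies no clear test of Hypothesis 3

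*Protocol*

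**What the plan says.** All references are to the protocol.

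- **Classes.** The process for Aim 3 analyses ARDS patients by PaO2/FiO2 "using 3 classifications: mild (201-300), moderate (101-200), and severe" (≤ 100). The Research Strategy for Specific Aim 3 again lists only mild, moderate and severe.
- **Test.** The process for Aim 3 continues: "We will assess outcomes in the 4 hypoxemia sub-groups noted above using a stratified" Kaplan–Meier curve, with log-rank statistics for mortality. The research strategy repeats the log-rank and presents the three-way segmentation as what makes it possible.
- **Declared subject.** "This subgroup analysis will evaluate protocol implementation of the high versus low positive end expiratory pressure (PEEP) protocol and assess relationship with patient outcomes".
- **Hypothesis 3.** "A high PEEP strategy in patients with moderate to severe hypoxemia and ARDS will improve outcomes".
- **Allocation.** "Implementation of the high PEEP protocol will be based upon clinician discretion".
- **Target group.** The research strategy says "Then we will evaluate implementation of the high PEEP strategy and outcomes in the group of patients with ARDS" who have PaO2/FiO2 ≤ 200. It then states that the stratified analysis will directly show how hypoxaemia, treatment and mortality are related.
- **Aim wording.** Specific Aim #3 itself is milder: "Characterize protocol implementation of the high positive end expiratory pressure protocol (PEEP) and outcomes for mechanically ventilated patients with" moderate or severe hypoxaemia and ARDS.

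**The concern.** The log-rank is the only test tied to Aim 3. Its number of groups contradicts the definition a few sentences earlier, and its compared factor is left open. Two analysts could follow the text faithfully and answer different questions: whether mortality differs by severity of hypoxaemia, or whether it differs by PEEP strategy. Only the second concerns Hypothesis 3. As worded, the second has no control for the reasons a clinician chose high PEEP beyond the PaO2/FiO2 class.

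The research strategy expects Aim 3 to have a large influence on standard of care, inside the health system and abroad. A comparison that can be settled after the curves are seen, or read as causal when it is not, is a weak basis for that.

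**Working it through.** **1. The count.** Classes defined: mild, moderate, severe = 3. Stated: 4. The stated figure is not reproduced. Four arises only from groupings the text does not define:

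- moderate/severe × high/low PEEP: 2 × 2 = 4;
- the three classes plus one above 300: 3 + 1 = 4, but that class lies outside the PaO2/FiO2 ≤ 300 group examined for ARDS.

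All three classes crossed with PEEP give 3 × 2 = 6. The choice changes the test (groups − 1 degrees of freedom). Three groups give 2 df (5% critical value 5.99) and four give 3 df (7.81). High versus low PEEP within moderate and severe gives 1 df over 2 strata.

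**2. The compared factor.** For severity: outcomes are assessed in hypoxaemia sub-groups, the segmentation is what enables the log-rank, and mild patients are included although Hypothesis 3 leaves them out. For PEEP: high versus low PEEP is the declared subject of the same paragraph, the curve is called stratified, and the research strategy mentions treatment. Neither log-rank sentence settles it.

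**3. If severity classes are compared.** The null hypothesis is equal survival across classes and contains no PEEP term. Illustration, all inputs assumed: 500 moderate and 500 severe patients, PEEP split 50:50 at random, follow-up to day 90, two-sided 5%, 300 runs. Hazard multipliers of 0.8 against 1.2 and 0.6 against 1.4 give hazard ratios of 0.67 and 0.43.

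| PEEP hazard ratio | Class log-rank, mortality 30%/30% | Class log-rank, mortality 25%/40% | PEEP log-rank stratified by class |
|---|---|---|---|
| 1.0 | 3% | 100% | 5–7% |
| 0.67 | 7% | 100% | 95–96% |
| 0.43 | 6% | 100% | 100% |

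The simulation error at 5% is √(0.05 × 0.95/300) = 1.3 percentage points, so 3–7% is compatible with 5%. The class test follows the severity gradient, not PEEP.

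A real benefit can even work against it. Assume class mortality of 30/33/40% and high PEEP, with hazard ratio 0.80, used in half of moderate and severe patients. Mortality becomes ½[m + 1 − (1 − m)^0.8]:

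- moderate: ½[0.33 + 1 − 0.67^0.8] = ½[0.330 + 0.274] = 30.2%;
- severe: ½[0.40 + 1 − 0.60^0.8] = ½[0.400 + 0.336] = 36.8%.

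The gap between classes narrows. With 100 to 300 per class, rejection falls from 26–66% (no PEEP effect) to 18–43%. These are not error rates; they show that the result does not answer Hypothesis 3.

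**4. If high and low PEEP are compared within classes.** The test is then relevant but controls only for PaO2/FiO2 class. Illustration, all inputs assumed: no PEEP effect, class-average mortality 30%/40%, 150 or 300 per class, and a binary severity factor present in half of each class.

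- Selection unrelated to prognosis within class: 4.8% and 5.8% significant, two-sided.
- Sicker patients given high PEEP more often (60–65% against 35–40%; severity hazard ratio 1.5–2.0): significant apparent harm in 6–31%.
- Sicker patients given it less often, same figures: significant apparent benefit in 7–29%.
- Stratifying fully on that severity factor: 4.5–6.2%, two-sided.

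The documents support none of these selection patterns over another, so neither the direction nor the size of bias is known.

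**5. Scale.** The protocol says "approximately 500 patients meet the criteria for" severe hypoxaemia in 2014. Table 4 sums to 3,421 and the text gives about 3,500 a year, so 500/3,500 = 14.3% and 500/3,421 = 14.6%. Table 5 splits 4,127 = 1,785 before + 2,342 after each site's gap. That gives 2,342 × 14.3–14.6% ≈ 335–342 severe patients after implementation, before the radiograph criterion. It assumes that the 500 share a denominator with those totals, which the protocol does not say.

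**The case against.** The best defence is that the PEEP comparison is a natural reading. The paragraph announces high versus low PEEP as its subject, and a stratified curve fits hypoxaemia as the stratifier. This stands. A reader might infer that Aim 3 as written does not test Hypothesis 3 at all; the documents do not support that, because it holds only if severity classes are what is compared. Likewise, 4 may be an intended 2 × 2 grouping and not a slip.

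It also stands that Aim 3 is partly descriptive: its own wording is to characterise, and the PEEP item among the secondary outcomes is a process measure. Yet Hypothesis 3 asserts improved outcomes, and the research strategy opens by speaking of efficacy, so the protocol reaches beyond description.

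Covariates for a secondary aim are commonly left to an analysis plan, and their absence alone would be no finding. What the protocol does fix is a log-rank whose only named control is hypoxaemia class, together with a claim about what it will show. The confounder adjustment in Data Analysis is described for the model of ventilator-free days, not for this test.

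Finally, every rejection rate above rests on assumed inputs. That is right: they show mechanism and direction, not the size of any error in this study.

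**Conclusion.** The point holds as an ambiguity plus an unsupported claim. The contradiction between three and four groups and the unstated compared factor can be read from the text and need no assumption. It follows by logic that a severity comparison cannot test Hypothesis 3. It follows from clinician discretion, in a study that the consent-waiver section calls purely observational, that a PEEP comparison controlled only for PaO2/FiO2 class is open to confounding by indication in either direction. On neither reading is a direct demonstration of a treatment relationship justified.

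How large the bias would be cannot be derived from the documents. The target population is not in doubt (PaO2/FiO2 ≤ 200), and the primary analysis of ventilator-free days is untouched. The change should be made, but no primary conclusion depends on it.

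**What to change.** 1. Correct 4 to the three defined classes, or define the fourth group.
2. State that Hypothesis 3 is assessed by comparing the high with the low PEEP protocol on mortality in ARDS patients with PaO2/FiO2 ≤ 200. Use a mortality model, for example a stratified Cox model, stratified by or adjusted for baseline PaO2/FiO2 and adjusted for available patient covariates, hospital and time. Report the result as an association and acknowledge residual confounding.
3. State that Kaplan–Meier curves by hypoxaemia class are descriptive, and change *directly show* to *describe*.

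Alternatively, label the whole of Aim 3 descriptive, in line with its own verb, and state that Hypothesis 3 is not formally tested.

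Cost: the descriptive option is wording only. The other adds one model. The covariate, hospital and time terms in Data Analysis belong to an identity-link model for ventilator-free days, so they must be carried into a mortality model, not reused as they stand. Adjustment will be incomplete: the listed data elements include age, gender, diagnosis codes and blood gases but no severity score.

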Title: Implementation of Lung Protective Ventilation in

Patients with Acute Respiratory Failure

(IMPROVENT)

Location: All 11 Intermountain Healthcare hospitals that manage

mechanically ventilated patients

PI: [name]

Sponsor: Pulmonary and Critical Care Department

Co-Investigators:

[name] MD MS [name] MD MS [name] MD [name] MD [name]

Research Coordinators:

[name] [name] [name] [name]

Regulatory Coordinators:

[name] [name] [name]

Data Analysts:

[name]
[name]

Statistician:

[name] [name]

Abbreviations, Acronyms and Symbols

ARDS	Acute Respiratory Distress Syndrome
ALI	Acute Lung Injury
PBW	Predicted Body Weight
ICU	Intensive Care Unit
ED	Emergency Department
STICU	Shock Trauma Intensive Care Unit
IMC	Intermountain Medical Center
POD	Persistent Organ Dysfunction
GLMM	Generalized Linear Mixed Model
EMR	Electronic Medical Records
VC	Volume Control
PRVC	Pressure Regulated Volume Control
MMV PRVC	Mandatory Minute Ventilation with Pressure Regulated Volume Control
SIMV/PS	Synchronized Intermittent Mandatory Ventilation Plus Pressure Support
VFD	Ventilator Free Days
ROSE	Reevaluation of Systemic Early Neuromuscular Blockade
PETAL	Prevention and Early Treatment of Acute Lung Injury
PEEP	Positive end Expiratory Pressure

Purpose of the Study and Hypotheses:

This is a quality improvement study with the purpose of observing and measuring the effects of implementation of a proven standardized lung protective ventilation protocol in the new electronic medical record system iCentra across all Intermountain Healthcare hospitals.

We hypothesize that implementation of a standardized computerized lung protective ventilation protocol across all Intermountain Healthcare hospitals will be feasible, will decrease initial tidal volumes to the target 6 ml/kg PBW, and will improve outcomes.

The objectives of this study are to:

- Determine if the implementation of lung protective ventilation (with a 6 ml/kg PBW tidal volume ventilation protocol on initiation of mechanical ventilation) improves outcomes in patients with acute respiratory failure requiring mechanical ventilation
- Determine if the implementation of lung protective ventilation (with a 6 ml/kg PBW tidal volume ventilation protocol on initiation of mechanical ventilation) improves outcomes in the sub-group of patients with the acute respiratory distress syndrome (ARDS)

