Intermountain Healthcare will implement a computerized version of the ARDS Network 6 ml/kg PBW ventilation protocol in their new electronic medical record system from Cerner, called iCentra. This computerized ventilation, oxygenation, and weaning protocol will become the default mechanical ventilation protocol for use on all intubated patients at Intermountain Healthcare hospitals. Physicians will be free, however, to decline to use the computerized mechanical ventilation protocol and to provide instead alternative orders for mechanical ventilation. The computerized ventilation, oxygenation, and weaning protocols will be separated so that physicians may select any combination of the protocols for patient care. It is expected that most mechanically ventilated patients will be managed with the combination of ventilation, oxygenation, and weaning protocols. However, patients with elevated intracranial pressure may be excluded per the attending physician discretion from the 6 ml/kg PBW ventilation protocol. The oxygenation protocol will target a partial pressure of arterial oxygen (PaO₂) of 55 to 67 mm Hg with a normal PEEP protocol using the ARDS Network low PEEP table or alternatively, for patients with moderate to severe ARDS, a high PEEP protocol based on the ARDS Network high PEEP table (Table 2).14 There is also a high range oxygenation protocol targeting a PaO₂ of 68 to 80 mm Hg for patients with hypoxic brain injury or ischemia of other organs in which the physician may prefer a higher oxygen partial pressure.

Based on a meta-analysis of high versus low PEEP clinical trials, there is a mortality benefit using a high PEEP strategy in patients with moderate to severe ARDS.¹⁵ Uncertainty exists, however, in how to implement a high PEEP strategy¹⁶ and review of the application of PEEP to patients enrolled in the ARDS Network 2 studies after publication of the meta-analysis do not show widespread adoption of a high PEEP strategy (**Figure 2**). Completed clinical trials of patients with moderate to severe ARDS, however, have safely employed a high PEEP strategy with good clinical outcomes¹⁷, and the proposed trial "Reevaluation Of

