Those to be enrolled must have respiratory failure requiring intubation and initiation of mechanical ventilation. Patients will be divided into two different groups: those patients who are managed with the computerized lung protective ventilation protocol as ordered by the attending physician and those patients managed with physician specified mechanical ventilation settings.

Compensation

Subjects will not be compensated for participating in this study.

Sample Size

The minimum sufficient sample size to detect a significant change in VFD was computed across a range of effects and heterogeneity. We estimate about 3,900 subjects would be sufficient to detect a 1.5-day increase in mean VFD with 80% power (*ICC* = 0.10) from a baseline of 21.9 VFD (SD=7.8) with a one-tailed test (**Table 3**).

Table 3. Minimum sample size for increase in mean VFD

ICC	1 day	1.5	2 day
		day	
0.01	6,800	3,200	2,300
0.10	8,500	3,900	2,300
0.20	8,300	4,000	2,400

The baseline VFD data for the power analysis was based on reported data from a meta-analysis of the association between tidal volume size and sedation needs

in patients without ARDS²⁵ among those who received initial tidal volumes between 6 and 10 ml/kg PBW – a demographic representative of our study population. The power analyses accounted for expected imbalance of patient enrollment (**Table 4**),^{26,27} heterogeneity among clusters,²⁸ and allowed for a variety of time effects (**Equation 1**).²⁹ This avoided artificial inflation of power at the study design stage.³⁰

The VFD y_{ikt} for each patient were simulated via a linear equation adapted from Hussy *et al.*³¹ with the addition of quadratic time effects:

$$y_{ikt} = \mu + \alpha_k + \beta_1 t + \beta_2 t^2 + \theta x_{ikt} + e_{ikt},$$
 (1)

where μ and e_{ikt} , were derived from the distribution of VFD reported in the metaanalysis by Serpa Neto *et al.*²⁵, θ varied from 1 to 2 per [name]'s instructions, α_k are the hospital-level random intercepts, $\beta = (\beta_1, \beta_2)$ is a vector of quadratic time effects, x_{ikt} is the initial tidal volume size for the *i*th subject in the *k*th cluster at time *t*.

	Volume	Proportion
McKay-Dee	542	0.1584
Utah Valley	608	0.1778
American Fork	68	0.0199
Dixie	479	0.14
Valley View	60	0.0175
IMC	1409	0.4119
LDS	206	0.0602
Riverton	49	0.0143

Table 4. Volume of mechanically ventilated patients in 2014

Methods/Procedures:

Research Strategy for Specific Aims 1 and 2

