Generalized linear mixed models (GLMM) with hospital-level random intercepts and an identify link function will be used to measure the effect of initial tidal volume size on VFD. It is proposed to measure the treatment as a continuous variable (rather than as a dichotomous indicator of whether the mechanically ventilated patient was cared for at a post-intervention site) in order to account for the variable "usual care" practices of tidal volume size. The protocol will be phased sequentially in a non-randomized phased implementation manner. Since it is hypothesized that the bundle will improve care and, resultantly, decrease duration of time on ventilator, statistical significance will be determined by a one-tailed, 5% significance test. Heterogeneity among clusters will also be measured and accounted for random intercepts. Potential secular trends will be adjusted for by inclusion of quadratic time effects, which would capture a variety of time effects – from linear to bell-shaped. Patient-specific confounders will be controlled for by additive inclusion of a matrix of patient-level covariates.

Mitigation Plans and Interim Analysis

We plan an interim analysis for futility and efficacy at the end of the third step, following the successful phasing in of the second cluster. If the mean VFD following implementation of the bundle is equivalent to the mean VFD prior to implementation (according to the two one-sided test procedure with 99% confidence having an equivalence margin of four hours) then futility will be declared and further data collection will cease. Conversely, if the mean VFD following implementation has increased by more than 2 days (according to a one-sided hypothesis test with 99% confidence), efficacy will have been established and further data collection will also cease.

Data Sharing:

Development of the ventilation protocol in iCentra for mechanical ventilation will likely increase the number of VFDs, decrease healthcare utilization and decrease cost. To ensure that the proposal deliverables are met, we have designed the following dissemination plan:

Internal Strategic Planning

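### The 80% power at 3,900 patients is stated for a shift in mean VFD, but the primary test is of a slope on initial tidal volume

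*Protocol*

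**What the plan says.** Four places in the protocol bear on this; no statistical analysis plan was available.

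- **Sample Size, text and Table 3.** The text says that "about 3,900 subjects would be sufficient to detect a 1.5-day increase in mean VFD with 80% power", at ICC 0.10, baseline 21.9 VFD, SD 7.8, one-tailed. Table 3 is titled "Minimum sample size for increase in mean VFD" and has columns for 1, 1.5 and 2 days.
- **Sample Size, Equation 1.** VFDs were simulated from hospital random intercepts, linear and quadratic time, and a term theta times x. The protocol says that x "is the initial tidal volume size for the" individual subject, and that theta "varied from 1 to 2 per" an investigator's instructions. It gives no unit, centring or reverse coding for x, and no unit for theta.
- **Data Analysis.** The mixed model is to "measure the effect of initial tidal volume size on VFD", tested one-tailed at 5% with quadratic time. The exposure choice is explicit: "It is proposed to measure the treatment as a continuous variable (rather than as a dichotomous indicator" of post-intervention care.
- **Purpose and Significance.** The hypothesis is that the protocol "will decrease initial tidal volumes to the target 6 ml/kg PBW, and will improve outcomes". Use is voluntary: "Physicians will be free, however, to decline to use the computerized mechanical ventilation protocol".

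**The concern.** The sample size is expressed in one parameter and the test estimates another. A step in mean VFD at go-live and a slope per unit of tidal volume coincide at only one size of change in mean tidal volume. That change depends on how many clinicians adopt the protocol, which is left to them and is not quantified in the power analysis.

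The precision of the two estimates also has different sources. A go-live step is estimated from before/after contrasts within hospitals and is partly confounded with calendar time. A slope on individual tidal volume also draws on the patient-to-patient spread in every hospital and month, before and after go-live. The same numerical effect can therefore need very different numbers of patients.

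A reader thus cannot tell what the primary test can detect with about 4,000 patients. The figure is relied on elsewhere: Study Design uses it to set the 16-month duration, and the Waiver of Informed Consent section uses it to argue that consent is impracticable.

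**Working it through.** **Inputs from the protocol.** One-sided 5%, 80% power: z sum = 1.645 + 0.842 = 2.486. SD 7.8, ICC 0.10. Table 5: 8 hospitals, washout months blank, 4,127 patients (1,785 before and 2,342 after go-live). Table 1, ED plus ICU: 2,997 patients.

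**Assumptions not in the protocol.** x is in ml/kg PBW. Table 1 bins are placed at their midpoints (3.5 for the lowest, 14.5 for the highest). After go-live a share p of patients is set at 6.0 and the rest stay as in Table 1. Where a range is given, the low end takes 7.8 as the total SD and the high end takes it as the residual SD.

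**1. The plan's own figure.** Two means without clustering: total N = 4 × 2.486² × 7.8² / 1.5² ≈ 670. With a 0/1 go-live step on Table 5's matrix, a hospital random intercept and fitted quadratic time (generalised least squares, N scaled in proportion), the results against Table 3 are:

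| ICC | 1 day: computed / stated | 1.5 days: computed / stated | 2 days: computed / stated |
|---|---|---|---|
| 0.01 | 7,014–7,086 / 6,800 | 3,038–3,070 / 3,200 | 1,662–1,679 / 2,300 |
| 0.10 | 6,529–7,257 / 8,500 | 2,891–3,214 / 3,900 | 1,618–1,800 / 2,300 |
| 0.20 | 5,813–7,268 / 8,300 | 2,578–3,225 / 4,000 | 1,447–1,810 / 2,400 |

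Two of the nine cells agree to within about 5% (ICC 0.01, 1 and 1.5 days). At 3,900 patients and ICC 0.10 the standard error of the step is 0.520–0.548, so power for 1.5 days is Φ(1.5/0.520 − 1.645) to Φ(1.5/0.548 − 1.645), that is 89% to 86%. The step detectable at 4,000 is 1.28–1.35 days.

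**2. The test that is planned.** Table 1 gives mean 21,049.5/2,997 = 7.02 and SD 1.27 ml/kg. With no adoption, the slope rests almost wholly on this spread, so N ≈ (2.486 × 7.8 / (1.5 × 1.27))² ≈ 104 with residual SD 7.8, or 104 × 0.9 ≈ 94 with total SD 7.8. The full calculation on Table 5, with the same random intercept and quadratic time, gives:

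| Share set at 6.0 after go-live | Mean / SD after | N for slope of size 1.5 | Detectable slope at 4,000 |
|---|---|---|---|
| 0% | 7.02 / 1.27 | 94–104 | 0.23–0.24 |
| 50% | 6.51 / 1.03 | 114–127 | 0.25–0.27 |
| 100% | 6.00 / 0 | 200–222 | 0.34–0.35 |

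Over wider assumptions (spread within hospital and month 0.5 to 1.25 ml/kg, fall in mean 0 to 1.1 ml/kg), N for a slope of 1.5 runs from 93 to 602. No assumed case comes near 3,900.

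**3. From slope to mean shift.** Shift = slope × fall in mean tidal volume.
- p = 100%: 1.5 × (7.02 − 6.00) = 1.54 days with unrounded means.
- p = 50%: 1.5 × (7.02 − 6.51) = 0.77 day.

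**4. Sign and scale as printed.** Theta is positive and multiplies tidal volume, so higher tidal volume yields more VFDs, the reverse of the hypothesis. If x is uncentred and μ is 21.9, expected VFD at 7.0 ml/kg is 21.9 + 1.5 × 7.0 = 32.4, above the 28-day maximum. Read literally in ml/kg, Equation 1 is therefore unlikely to be the model that was run. The sign does not change N.

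**The case against.** The strongest reply is that Table 3 means what its title says: a before/after shift was powered, x in the simulation was probably a 0/1 indicator or a reduction in tidal volume, and its printed definition is a labelling slip. The step model gives numbers of the right order and comes close in two cells. Table 3 is rounded, comes from simulation and is not monotone in ICC (8,500, then 8,300), so gaps do not prove a different model. This is plausible. It concedes, however, that Equation 1 is misdescribed, and it leaves Data Analysis testing something other than what was powered.

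Second, the unit is hardly obscure, since the protocol reports tidal volume in ml/kg PBW throughout. Significance also makes the computerized protocol the default and expects most patients to be managed with it; near full adoption the slope of 1.5 gives about 1.5 days. It is fair that the 0% and 50% cases are illustrations without a source in the protocol. But the power analysis states no adoption level, and even at 100% adoption the slope needs 200–222 patients, not 3,900.

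Third, nothing in the design need change: the step has 86–89% power at 3,900, and on the ml/kg reading the slope has ample power. That stands, and it limits the point to a wrong statement of power. It is also true that 3,900 is not shown to be an arithmetic error, because the simulation's time effects and tidal-volume distribution are not given.

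**Conclusion.** The point holds. The stated 80% power at 3,900 patients belongs to a shift in mean VFD and is not the power of the primary test, which estimates a slope on continuous tidal volume. The gap is large: about 94–222 patients for a slope of 1.5 per ml/kg, against about 2,900–3,200 for a 1.5-day step and 3,900 as stated. With 4,000 patients the detectable effect is about 0.23–0.35 VFD per ml/kg for the slope, or 1.28–1.35 days for the step.

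The slope figures rest on the assumed ml/kg unit, the Table 1 midpoints and the assumed adoption shares, and are before adjustment for patient covariates. The mismatch itself rests on the text alone. The positive sign and missing unit in Equation 1 are minor errors of the same origin. None of this shows that the study is underpowered.

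**What to change.** 1. In Equation 1, correct the definition and unit of x (and any centring or reverse coding), and the sign and unit of theta.
2. Make the powered parameter and the Data Analysis parameter the same. Either power the tidal-volume slope, stating the assumed tidal-volume spread and adoption before and after go-live, or make the go-live indicator the primary exposure and power that.
3. Re-run the simulation, state the time effects used, and restate Table 3 and the power or detectable effect at about 4,000 patients.
4. As a minor addition, vary the SD in the re-run. The 21.9 (SD 7.8) comes from patients without ARDS, while the eligibility criteria do not exclude ARDS; the protocol does not give the size or direction of any difference.

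The cost is one simulation re-run, a corrected Equation 1 and Table 3, and one sentence in Sample Size or Data Analysis. No extra enrolment is needed.
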